Secondary outcomes: Our second aim is to assess the extent to which carers engage with the platform (i.e., site usage information) is associated with improvements in expressed emotion, perceptions of caregiving, coping strategies, loneliness, social support, self compassion, mindfulness, and mood symptoms. We also plan to examine the associations between carers' involvement in Altitudes and their loved one with FEP's use of emergency services (e.g., ED visits). We will compare outcomes from the Altitudes and control groups to examine any improvements experienced by participants who engaged with the platform compared to routine clinical care.

Exploratory outcomes: We would like to explore rates of trauma symptoms related to experiencing and providing support for a loved one who experienced an initial psychotic episode. One of the exploratory aims is to examine the extent to which their loved one's initial psychotic episode and related experiences (e.g., psychiatric hospitalizations, changes in work/school engagement, etc.) might be associated with trauma-related symptoms. We are also interested in the extent to which engagement in Altitudes might promote post traumatic growth among caregivers of a young person with FEP. Trauma and post traumatic growth from caregivers in the treatment group will be compared to controls to assess the extent of impact of Altitudes on these outcomes.

Safety Evaluations

A safety plan for Altitudes was developed before participants joined the digital platform by research staff based on previous experience with digital interventions. All safety measures were approved by the director of each participating NC FEP clinic.

Statistical and Analytic Plan

Primary Outcomes: For Aim 1, we will use descriptive statistics to examine carers' perceptions of the Altitudes platform and clinical moderators via four brief questionnaires: the Altitudes Health Care Climate Questionnaire (A-HCCQ), Altitudes Usability Questionnaire (AUQ), Altitudes Perceived Competence Scale (A-PCS), and Working Alliance Inventory for Guided Internet interventions (WAI-I, Gomez Penedo et al., 2019). Additionally, descriptive statistics will assess interactions with the platform to evaluate acceptability and engagement (e.g., logins, posts, reactions, completed activities, etc.) with the platform (i.e., acceptability and usability).

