Information gathered in the post-treatment qualitative interview will be analyzed to identify participants' thoughts about the usefulness of Altitudes as well as feedback to improve the intervention for others. Qualitative analysis will be conducted on the feedback interviews using grounded theory. As with qualitative analysis, a codebook will be developed by the research team in which thematic analysis of all interviews will conducted. The codebook will include themes and subthemes with a focus on the different perceived strengths of the intervention as well as areas that need improvement.

Secondary Outcomes: The platform will collect information about frequency of engagement with Altitudes (i.e., site usage). Psychosocial outcomes will be summarized within and between conditions using univariate statistics (e.g., means, standard deviations). To evaluate change over time on psychosocial outcomes, we will utilize linear mixed models (LMM) including fixed effects of time, group, and group x time interactions and random effects at the participant level. We will calculate changes from baseline at each time point using least-squares means and standardized least-squares mean differences to estimate within- and between-group changes, respectively. To estimate magnitude of change from baseline, we will calculate effect sizes. We will explore the relationship between baseline characteristics (e.g., age, gender) and engagement data (i.e., site usage information) on any changes in psychosocial outcome measures from baseline to midpoint and posttreatment using multiple linear regression. We will use Pearsons correlation coefficients to examine associations between carers' involvement in Altitudes and their loved one with FEP's use of emergency services (e.g., ED visits). If possible based on sample size, we will dichotomize engagement data (site usage) between low engagement and high engagement before comparing site usage with emergency service utilization.

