As this platform will be provided as an adjunct to CSC clinical care, pertinent clinical impressions and other relevant clinical information will be shared with the individual's clinical team at their respective FEP clinic.

All individual interviews will be conducted virtually via secure Zoom and will be led by the Altitudes study coordinator and/or a graduate student in clinical psychology at UNC-Chapel Hill. All feedback sessions will be digitally recorded, and will be de-identified and transcribed by a member of the research team or a transcription service. The purpose of these recordings and transcriptions is to allow the research team to examine the feedback provided in the interviews for the purposes of improving the platform to better support families and caregivers in supporting their loved ones experiencing psychosis via psychoeducation and skills such as healthy coping mechanisms.

Subjects

Up to 30 total Altitudes participants will be recruited from two of the FEP clinics in North Carolina (OASIS & SHORE) as it is a pilot study, specifically family members of individuals experiencing FEP. An additional 30 control participants will be recruited from three other FEP clinics in North Carolina (Eagle, Encompass, and AEGIS). All participants will have a loved one currently enrolled in or recently graduated from a CSC program. Demographic and clinical information that will be collected as self-report for possible use as covariates includes: 1) participant demographics: age, sex/gender identity, race/ethnicity, level of education, current zip code, relationship to loved one, employment status, proximity to the loved one with psychosis (e.g., cohabitating, living in different states), hours of contact with loved one per week on average, number and ages of any other children; and 2) young person with psychosis' demographics and relevant clinical information: age, sex/gender identity, level of education, stage of recovery, and level of education.

Eligibility Criteria

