The research study coordinator will communicate with clinicians and other members of the treatment team to explain the project and discuss eligibility criteria for the study. If agreed to by the clinical team at each site, the research team will attend the beginning or end of multifamily group (MFG) sessions at OASIS & SHORE to provide an overview of Altitudes and answer any questions that potential participants might have about the study. Research staff will additionally contact the other three clinics (Eagle, Encompass, AEGIS, and We2Care) about control participants and attend their MFG to provide information to prospective participants. Clinical team members will be asked to review their current caseloads to identify potentially eligible participants (i.e., parents and caregivers of patients who are currently receiving services or recently graduated from one of the programs). The study coordinator and/or research assistant (RA) will engage in discussion with the treatment team to help identify appropriate individuals for inclusion in the project. When participants have been identified and expressed interest in participation to their clinician or other treatment provider, the research study coordinator or RA will reach out to the individual in their preferred method of contact (i.e., in person at the clinic or via phone/email) to discuss the project and complete an initial screen to confirm the inclusion and exclusion criteria. Participants will then be

given the highlights of the study and their participation via phone after their screening. Highlights will include the study, its aims, what they will be asked to do, the timeframe of their participation, and that it is completely voluntary and they can withdraw consent at any time, for any reason, without penalty. Additionally, in the email to review the document and at the top of the consent forms in DocuSign there will be a phone number for them to contact and explicitly state to call the number if they have any questions prior to signing the documents.

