1. Descriptive statistics examining Site Usage Information [Time Frame: Duration of the trial, from onboarding at baseline through post-treatment]

The Altitudes platform passively collects engagement data, including the number of therapeutic pathways started and completed as well as any posts or comments made on the platform. We will provide mean and standard deviation scores for each site usage category, as well as a range, for the Altitudes group only. Depending on sample size, we will categorize users in low or high engagement groups.

2. Mean Change in UCLA Loneliness Scale Score [Time Frame: Baseline, Post-treatment, up to 14 weeks]

The UCLA Loneliness scale is a 20-item scale. Answers are on a 4-point scale with options "I often feel this way," "I sometimes feel this way," "I rarely feel this way," and "I never feel this way." Possible scores range from 20 to 80. Higher scores reflect worse outcomes (greater feelings of loneliness). The UCLA Loneliness Scale is a part of the PhenX Toolkit.

3. Mean Change in Multidimensional Scale of Perceived Social Support - total score [Time Frame: Baseline, Post-treatment, up to 14 weeks]; Alternative form for Altitudes participants, original form for control group.

The MOS Social Support Survey is a 16-item scale. Answers are on a 7-point scale with options ranging from "very strongly disagree" to "very strongly agree". Possible scores range from 16 to 112. Higher scores reflect higher feelings of social support (more perceived social support).

4. Mean Change in the Experience of Caregiving (ECI) Score [Time Frame: Baseline, Post-treatment, up to 14 weeks]

The Experience of Caregiving (ECI) Scale is a 66-item scale. Answers are on a 5-point scale starting at 0 with options "never," "rarely," "sometimes," "often," and "nearly always". Possible scores range from 0 to 264. Higher scores indicate greater feelings of preparedness for caregiving whereas lower scores reflect feeling less prepared to provide caregiving.

5. Mean Change in Family Questionnaire of Expressed Emotion - Total Score [Time Frame: Baseline, Post-treatment, up to 14 weeks]. The Family Questionnaire of Expressed Emotion is a part of the PhenX Toolkit.

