In addition, users will be able to "switch off" their profile and hide all of their existing comments on the system should they become concerned about their privacy during their course of participation. The limits of the moderator to respond (e.g., in a timely manner to emergencies) will also be fully explained. In order to protect the privacy of users who discontinue using the system, any accounts that have not been activated for one month may be deactivated following a follow-up telephone call from a moderator. Specifically, our disengagement protocol states that a participant will receive an email/call/text message if they have not logged onto the platform for two weeks. If another two weeks pass, we will call this person to check in about any potential issues or concerns. As noted

above, the moderation team will check in with participants on a monthly basis to ensure they are able to navigate the site with ease and to answer any questions they might have about the platform and any of its components/capabilities. Participants can opt out of these regular check ins from moderators at any time. If participants do not comply with the guidelines for safe use of Altitudes (e.g., discriminatory comments towards other users; disclosing identifying details of the identified patient) they will be excluded from the system.

Clinical safety: Although highly unlikely for the parent or caregiver, it is possible that participants may post information indicative of a clinical risk in their loved one, although participants will be advised that the service cannot respond to emergencies. Nonetheless, clinical risk will be monitored through manual and automated procedures. Information related to clinical risk will be screened daily by moderators and/or research staff. This information can include: 1) posts made by participants, which disclose evidence of deterioration in mental state of the young person in the care of participants; 2) participants reports or complaints on posts made by other users; and 3) automatically detected and blocked words posted by participants in the system. Additionally, clinical and family peer moderators will analyze the 'Community' feed to ensure that misinformation and falsehoods are not being spread by users of the platform.

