The research team will respond according to a *risk management algorithm*, which outlines the required response to potential indicators of clinical risk in terms of the source of the information. If the online moderator becomes aware of potential indicators of risk in the online application they will conduct an initial risk assessment, make the appropriate clinical response and inform the supervisor. If the study research coordinator becomes aware of an indicator of clinical risk they will inform their supervisor who will again respond clinically. The principal investigator will assess the criteria for withdrawal and potential suspension of usage restriction to a user's Altitudes account. The principal investigator will have ultimate responsibility for withdrawing participants from the study or restricting their Altitudes account.

Reporting of adverse events

Any adverse outcomes for participants, such as exposure to potentially harmful interactions through social networking, will be reported to University of North Carolina at Chapel Hill's (UNC-CH) Institutional Review Board (IRB). If a participant informs the moderators of an adverse event relating to the young person in their care or of any signs of deterioration in their mental health, the Altitudes moderators will communicate with the relevant clinicians where indicated.

RECRUITMENT STRATEGY

For recruitment, research staff have partnered with CSC clinics in previous studies and consultation. For this reason, research staff have extensive knowledge regarding recruiting from this target population. Research staff will inform the CSC providers and PSS about the study and its eligibility criteria to allow the treatment team the ability to identify potentially eligible participants. The treatment team will then approach potential parent and caregiver participants to gauge their interest in participating on the digital platform. If the person expresses interest or would like to know more about the study, the provider or PSS will pass along their information to research staff via referral forms to contact them to further discuss specifics about the study (e.g., describe the social networking and educational aspects of the platform). If the individual is still interested in participating, the client will be screened for eligibility. Upon meeting eligibility criteria, the individual will be scheduled for a baseline visit.

CONSENT PROCESS

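### The change-score regressions for platform engagement discard the partial data of carers lost after midpoint; a usage-by-time mixed model, with usage suitably defined, would keep them

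*Combined protocol and SAP*

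**What the plan says.** The Synopsis (Evaluations, Secondary outcomes) sets the question: "Our second aim is to assess the extent to which carers engage with the platform (i.e., site usage information) is associated with improvements" in a list of psychosocial measures. The Statistical and Analytic Plan (Secondary Outcomes) answers it by exploring the effect of baseline characteristics and site usage "on any changes in psychosocial outcome measures from baseline to midpoint and posttreatment using multiple linear regression". The paragraph on Exploratory Outcomes plans the same exploration for trauma symptoms and post-traumatic growth but names no model for it.

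The same Secondary Outcomes paragraph handles the group comparison differently, with "linear mixed models (LMM) including fixed effects of time, group, and group x time interactions and random effects at the participant level". That model contains no usage term.

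Only Altitudes carers have usage data, and the Subjects section caps them: "Up to 30 total Altitudes participants will be recruited from two of the FEP clinics in North Carolina". The Data Analytic Plan (Secondary Outcome Measures, item 1) gives the time frame for usage as "Duration of the trial, from onboarding at baseline through post-treatment". No section states an expected dropout rate, a missing-data method, an analysis set or a sensitivity analysis.

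The plan does foresee carers leaving or going quiet. Screening Procedures and Consent Process tell carers that "they can withdraw consent at any time, for any reason, without penalty". Under Online safety, "any accounts that have not been activated for one month may be deactivated following a follow-up telephone call from a moderator".

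**The concern.** A change score exists only when both visits exist, so ordinary regression on it drops any carer without the later visit. For a carer lost after midpoint, the study already holds a baseline score, a midpoint score and a usage log, yet the post-treatment regression uses none of them. The plan adopts a model that keeps such partial records for the group question but not for the engagement question, which is itself the second aim.

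The stakes are modest but real. The Power Analysis section says that the pilot is meant to inform larger trials. A usage slope that is flattened, or less precise than the data allow, would feed into that planning.

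**Working it through.** **There is no figure in the plan to reproduce.** The Power Analysis section reports no calculation, and no dropout rate, effect size or SD is given. Everything numerical below is illustration on stated assumptions.

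**Step 1. Who enters each analysis.**

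| Carer's visits | Midpoint regression | Post-treatment regression | Mixed model with usage x time |
|---|---|---|---|
| All three | in | in | in |
| Lost after midpoint | in | out | in, with two scores |
| Misses midpoint only | out | in | in, with two scores |
| Baseline only | out | out | one score, adds little |

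**Step 2. Precision.** The correlation detectable with 80% power at two-sided 0.05 is r = tanh[(1.960 + 0.842)/√(n − 3)].

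- n = 30: tanh(2.802/5.196) = 0.49
- Assumed dropout of 10/20/30/40% leaves n = 27/24/21/18, giving 0.52/0.55/0.58/0.62

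**Step 3. Dropout that depends on usage alone.** In a large-sample simulation with a true standardised slope of 0.40, the completers' slope stays at 0.40. At 20% dropout the SD of usage among completers falls to 0.90, so the correlation becomes 0.40 × 0.90/√(0.40² × 0.90² + 0.84) = 0.36/0.985 = 0.37. Range and precision are lost, but the slope is not biased.

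**Step 4. Dropout that depends on usage and on midpoint change.** Assumptions: n = 30; visit correlations 0.70 (baseline-mid), 0.60 (baseline-post) and 0.75 (mid-post); usage effects 0, 0.15 and 0.30 SD at the three visits; logistic dropout after midpoint, more likely with low usage and poor midpoint change; usage fully known. The true slope for post-treatment change is 0.30.

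| Dropout before post-treatment | 14% | 23% | 31% | 37% |
|---|---|---|---|---|
| Change-score regression, as planned | 0.26 | 0.25 | 0.23 | 0.22 |
| Same, with baseline score added | 0.27 | 0.26 | 0.25 | 0.24 |
| Mixed model, random intercept only | 0.28 | 0.28 | 0.28 | 0.27 |
| Likelihood, unrestricted covariance | 0.30 | 0.30 | 0.30 | 0.30 |

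A separate run gave 0.23 to 0.25 for the planned regression at 21 to 32% dropout. The understatement is (0.30 − 0.25)/0.30 = 17% to (0.30 − 0.23)/0.30 = 23%. The empirical SE of the baseline-adjusted version is 0.188 at 22% dropout and 0.201 at 29%. So the bias is about 0.05/0.188 = 0.27 to 0.07/0.201 = 0.35 of an SE, and slightly less against the somewhat larger SE of the unadjusted regression.

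**Step 5. Does the repair work when usage is the total count?** Not cleanly. Usage is counted through post-treatment, so leaving early cuts the count short. In one illustration, with leaving unrelated to weekly rate, leavers averaged 24 logins against 48 for stayers. When leaving depended on midpoint change, a likelihood analysis using those truncated counts gave 0.33 to 0.35 against a true 0.30, and 0.04 to 0.06 when the true slope was zero. With usage taken as a weekly rate or as use up to midpoint, and an unstructured covariance, it gave 0.29 to 0.30 in every dropout scenario tried, with an SE about 2 to 10% smaller than the planned regression.

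**The case against.** A reader might infer that the least engaged carers fall out of the very analysis of engagement. The documents do not support that as a statement of fact.

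- Low platform use is not study exit. Visits are run by the study team over Zoom and compensated, and all participants are asked to attend all three. A low user who attends is kept.
- Closing an idle account is presented as a privacy measure; nothing says that it ends outcome visits. Nothing says that visits continue either.
- The investigator's power to withdraw carers ("The principal investigator will have ultimate responsibility for withdrawing participants from the study or restricting their Altitudes account") does not help. The withdrawal criteria in the protocol concern repeated inappropriate use, which is not low use.
- The consent wording is generic.

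It is also fair to say that loss related to usage alone leaves the slope unbiased. Bias needs a further assumption, that leaving depends on how the carer was doing, and the documents neither state nor exclude it. Even then the bias is a fraction of an SE in an unpowered exploratory pilot. And simply adding total usage to the mixed model would bring in an error of its own (Step 5).

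One could add that the midpoint and post-treatment regressions describe different carers, so their slopes cannot be compared. That is true, but the plan proposes no such comparison.

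All of these points stand, and they limit the size of the concern. They do not remove the core: the planned method discards scores already collected, no section supplies a remedy, and a better method in the same model family is available.

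**Conclusion.** The point holds as a minor improvement. What is certain from the documents is that the post-treatment regression uses nothing from a carer lost after midpoint, and that the planned mixed model does not address usage. What is conditional is the harm:

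- If dropout is unrelated to outcome, the cost is precision only.
- If it depends on both usage and midpoint change, the slope is understated by about 17 to 23% at 21 to 32% dropout, or a quarter to a third of one SE.

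Those sizes rest on assumed dropout rates, correlations and dropout strength. A claim that low users will leave, or that the engagement result will be biased, goes further than the documents allow. If leaving depends on post-treatment change that is never observed, a mixed model would not fully correct it either.

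**What to change.** In the Statistical and Analytic Plan (Secondary Outcomes), replace the two change-score regressions with one longitudinal mixed model in the Altitudes group, fitted to all available baseline, midpoint and post-treatment scores. Include time, usage, usage x time and the chosen baseline characteristics, and read the association from the usage x time terms at midpoint and post-treatment. Specify an unstructured covariance across the three visits, since a random intercept alone leaves some bias. Name the same model for the engagement exploration under Exploratory Outcomes, where none is given.

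Define usage for this model so that leaving early does not shorten it, for example as a rate per week of access or as use up to midpoint. Do not use the total count through post-treatment. If a rate is chosen, say how weeks after account deactivation are counted. It would also help to report usage for carers with and without each follow-up score.

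The cost is analysis wording and slightly more analysis work, with no new data or visits. The drawback is a three-visit covariance estimated from at most 30 carers. Carers with only a baseline score will still add little.

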Baseline: Parents or caregivers who are deemed eligible schedule a virtual appointment with the study coordinator to obtain informed consent and complete the baseline assessments (Demographics & psychological measures). Specifically, all participants will be asked to complete the Experience of Caregiving Inventory (ECI; Szmukler), the Family Questionnaire of Expressed Emotion (Wiedemann et al., 2002), Brief COPE (Carver, 1997), UCLA Loneliness Scale (Russell, 1996), Multidimensional Scale of Perceived Social Support (For control and Alternative form for Altitudes condition; Zimet et al., 1990), Modified Psychosis Attitudes Survey (PAS; Kopelovich et al., 2022), PTSD Checklist for DSM-5 (PCL-5, Weathers et al., 2013), Post Traumatic Growth Inventory (PTGI, Tedeschi & Calhoun, 1996), General Health Questionnaire-12 (GHQ-12; Goldberg, 1972), Self-Compassion Scale – Short Form (SCS-SF; Raes et al., 2011), and Five Facet Mindfulness Scale (FFMQ; Bohlmeijer et al., 2011). Additionally, all participants will complete a brief survey on engagement with services within the CSC program and outside the program (e.g., individual therapy, family groups outside of CSC, etc.). Altitudes condition participants are then oriented to the Altitudes platform if part of the open trial enrollment.

Study Treatment: Participants in the Altitudes condition will be given access to the digital platform Altitudes for approximately 6 months. Weekly engagement is decided by the participant. Digital access is available daily and digital access to family peer worker and online therapists is made available during their engagement with the platform. Control participants will have not interaction with the platform but may engage in routine clinical

care for parents and caregivers at CSC clinics, such as multifamily group and treatment planning sessions

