Exploratory Outcomes: We will use descriptive statistics (M, SD) to examine self-reported trauma symptoms among carers of individuals with FEP. Descriptive statistics (M, SD, & effect sizes) will also be used to examine any changes in posttraumatic growth from baseline to midpoint and baseline to post-treatment. We will evaluate change over time in trauma-related symptoms and post-traumatic growth both within- and betweengroups using LMMs in the same manner as specified in our analysis of secondary outcomes. We will explore the relationship between baseline characteristics (e.g., age, gender) and engagement data (i.e., site usage information) on any changes in trauma-related symptoms and posttraumatic growth orientation over time.

Data and Safety Monitoring Plan

Privacy and online safety will be managed in accordance with the 'Online social networking' guidelines published by 'Cybersmart', a national cybersafety and cybersecurity education program managed by the Australian Communications and Media Authority (ACMA). Online safety will be monitored by Altitudes moderators (clinicians involved in the project, family peer support workers, graduate students in the Department of Psychology and Neuroscience) with supervision from licensed clinical psychologists Drs. [name] and [name]. [name] will function as the Project Medical Officer.

INTRODUCTION

Background and Rationale

Psychosis is one of the most debilitating health conditions, both mental or physical disorders, with significant impact on the individual as well as their family and supports. In response to these psychiatric disorders, known as schizophrenia-spectrum disorders, and to circumvent poor outcomes, early intervention services for first episode psychosis

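### The engagement regressions model change from baseline without committing to the baseline score of the same scale, so regression to the mean can bias the usage slope in either direction

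*Combined protocol and SAP*

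**What the plan says.** In the Protocol Synopsis, under Evaluations, the second aim asks whether engagement "is associated with improvements in expressed emotion, perceptions of caregiving, coping strategies, loneliness, social support" and further outcomes. The analysis for that aim is in the Statistical and Analytic Plan, Secondary Outcomes. It begins "We will explore the relationship between baseline characteristics (e.g., age, gender) and engagement data (i.e., site usage information" and takes as its outcome "any changes in psychosocial outcome measures from baseline to midpoint and posttreatment using multiple linear regression". The Exploratory Outcomes paragraph repeats the idea for trauma symptoms and post-traumatic growth, but its engagement sentence names no method.

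Neither paragraph mentions the baseline score of the scale under analysis. The Subjects section introduces a list with "Demographic and clinical information that will be collected as self-report for possible use as covariates includes"; it contains carer demographics and the young person's demographics and clinical details, and no psychosocial scale score. The Data Analytic Plan section lists mean-change outcomes and gives no regression specification.

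The group comparison uses "linear mixed models (LMM) including fixed effects of time, group, and group x time interactions and random effects at the participant level". That model includes baseline as a time point but has no engagement term, so it does not serve the engagement question.

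On how usage arises, the Study Treatment paragraph says "Weekly engagement is decided by the participant". On numbers, the Subjects section says "Up to 30 total Altitudes participants will be recruited from two of the FEP clinics in North Carolina", so at most 30 carers have usage data.

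**The concern.** Change from baseline is negatively correlated with the baseline score whenever baseline and follow-up are imperfectly correlated, because extreme scores tend to move toward the mean on re-measurement. A predictor that is related to the baseline score inherits part of that movement. Usage is self-selected, so such a relation is plausible, although the documents do not measure it.

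This regression is the direct analysis of the engagement part of the second aim, and the Outcomes section hypothesizes that engagement will contribute to better coping and lower expressed emotion. A slope produced by regression to the mean could be read as supporting that hypothesis, or could hide a real association. The pilot is also meant to inform later, larger trials. Because the covariate list is open, analysts could fit the model with or without the baseline score, and the two can disagree.

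**Working it through.** The plan states no figure to reproduce. It gives no alpha, standard deviation, baseline to follow-up correlation or dropout rate, and says no power calculation was done. The size below therefore rests on assumptions.

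**Inputs.** From the documents: n = 30 at most; outcome is change; usage is chosen by the carer. Assumed: standardized scores with equal variance at both visits; ρ (baseline to follow-up correlation) 0.5 to 0.7; r (usage to baseline correlation) 0, 0.3 or 0.5, either sign; two-sided 5% test; no true usage effect; higher score is worse.

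**Case A: usage depends on the observed baseline score.** Follow-up is ρ × baseline plus independent error. The slope of change on usage, without the baseline score, is −r(1 − ρ), in scale SDs per SD of usage:
- ρ 0.5: −0.3 × 0.5 = −0.15; −0.5 × 0.5 = −0.25
- ρ 0.7: −0.3 × 0.3 = −0.09; −0.5 × 0.3 = −0.15
- r = −0.3, ρ 0.5: +0.15, an apparent harm
- r = 0: zero, no bias

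With the baseline score in the model the expected slope is zero. Simulation (5,000 runs per row, n = 30, two further covariates in each model):

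| ρ | r | Rejects, no baseline | Rejects, with baseline | SE, no baseline | SE, with baseline |
|---|---|---|---|---|---|
| 0.5 | 0 | 4.7% | 4.9% | 0.197 | 0.174 |
| 0.5 | 0.3 | 11.6% | 4.6% | 0.193 | 0.181 |
| 0.5 | 0.5 | 25.3% | 5.1% | 0.190 | 0.199 |
| 0.7 | 0 | 5.2% | 5.3% | 0.152 | 0.143 |
| 0.7 | 0.3 | 8.6% | 4.8% | 0.151 | 0.150 |
| 0.7 | 0.5 | 16.2% | 4.8% | 0.149 | 0.165 |

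Without the two further covariates, runs of the ρ 0.5, r 0.5 case gave 26% to 28%. The overall range is therefore about 9% to 28%. With 24 carers analysed (an assumption), the unadjusted rates are 10.3% and 20.0% at ρ 0.5, and 8.0% and 13.9% at ρ 0.7.

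**Precision.** Apart from sample-size factors common to both, the variance of the slope is proportional to (1 − ρ)²(1 − r²) + (1 − ρ²) without the baseline score, and to (1 − ρ²)/(1 − r²) with it. At r = 0 the ratio is (1 + ρ)/2, which is 0.75 at ρ 0.5. From the table at ρ 0.5, the SE changes as follows:
- r 0: 0.174/0.197 = 0.88, about 12% smaller
- r 0.3: 0.181/0.193 = 0.94, about 6% smaller
- r 0.5: 0.199/0.190 = 1.05, about 5% larger

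Setting the two variances equal gives a break-even |r| of about 0.46 at ρ 0.5 and 0.36 at ρ 0.7.

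**Case B: usage depends on a stable trait.** Both scores measure the same trait with independent error, so usage has correlation r with each. The change-score slope is then zero. The adjusted slope is r(1 − ρ)/(1 − r²), which at ρ 0.5, r 0.3 is 0.15/0.91 = 0.165. In simulation (ρ 0.5) the adjusted model rejects 14.7% at r 0.3 and 40.9% at r 0.5; the unadjusted change model rejects 5.1% and 4.7%. The ranking of the two models reverses.

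**The case against.** The strongest reply is that the plan is incomplete rather than wrong. A baseline scale score is a baseline characteristic, the list in "baseline characteristics (e.g., age, gender) and engagement data (i.e., site usage information" is only illustrative, and the Subjects list is for possible use. This stands. A reader might infer that the plan excludes the baseline score; the documents do not say so. They only fail to commit to it.

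A reader might also infer that the plan will manufacture a benefit. That requires worse-scoring carers to use the platform more, which the documents do not establish. The Background cites lack of time and access as a reason families miss family interventions, and the section on potential benefits describes carers with overfull schedules. If the most burdened carers use the platform less, the bias hides a benefit instead. This objection stands too: the direction is unknown and the bias may be absent.

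A third reply is that the baseline-adjusted model is not reliably better. Case B confirms this. Engagement is not randomized, and the data may not show which mechanism operates. It argues for reporting both models, and against leaving the choice open until the data are in.

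Finally, these are exploratory regressions in an unpowered pilot, with no alpha or decision rule attached. The rejection rates are therefore a yardstick for the bias, not the error rate of a test the plan defines. That limits the weight of the point without removing it, because the analysis answers a stated secondary aim.

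**Conclusion.** The point holds as a gap in specification with a conditional bias. The plan does not commit to the baseline score of the same scale. If self-chosen usage is related to the observed score, the unadjusted slope is off by 0.09 to 0.25 scale SDs per SD of usage in either direction, for ρ 0.5 to 0.7 and |r| 0.3 to 0.5. A nominal 5% test then rejects about 9% to 28% of the time at n = 30, against about 5% with the baseline score added. At r = 0 there is no bias.

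Two stronger readings are not supported. One is that adjustment always sharpens the estimate: the gain is confined to weak usage to baseline relations and becomes a loss at r 0.5. The other is that adjustment restores validity in general: it does so in Case A and fails in Case B. All values of ρ and r are assumptions. The primary feasibility outcomes and the between-group mixed model are not affected.

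**What to change.** In the Secondary and Exploratory Outcomes paragraphs of the Statistical and Analytic Plan:
- Pre-specify a regression of the midpoint score, and of the post-treatment score, on site usage plus the baseline score of the same scale. Name this method in the exploratory paragraph, which now names none for engagement.
- Fix at most one or two further covariates in advance, given at most 30 carers.
- Report the unadjusted change-score regression beside it as a sensitivity analysis, and say that the two answer differently depending on whether usage follows the observed score or a stable trait.
- Describe the result as an association, not a dose-response effect.

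The baseline scores are already collected from every participant. The cost is a few sentences, one degree of freedom per model, a second set of estimates to report, and the IRB approval that the protocol requires for analysis changes.
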